5.2 Secondary Efficacy Endpoints

- Cumulative Daily In-Hospital Pain Score: 0 (no pain) – 10 (most pain)

Pain Scores are a measure of the subject's postoperative pain that are recorded every four hours by the nursing staff. They are limited by the subject's perception of pain, concomitant pain medication use, and correlation with an abstract scaling system.

- Mean Time to First Opioid Use (hours)

Time to first opioid use is a surrogate marker of postoperative pain. It is limited by variations in anesthesiologist intraoperative analgesia techniques.

- Mean Time to Ambulation (hours)

Time to ambulation is a downstream marker of postoperative pain control. Ambulation is limited by subject motivation and/or physical disability.

- Pulmonary Complications: Pneumonia and Atelectasis requiring Bronchoscopy (y/n)

Pulmonary complications are a downstream marker of postoperative pain control as subjects with chest wall postoperative pain commonly splint with respiration. Splinting is associated with atelectasis and pneumonia.

- Liposomal Bupivacaine and Stand Bupivacaine Adverse Events (y/n):

- Gastrointestinal- nausea, emesis, constipation
- Hypersensitivity- pruritis, urticaria, anaphylaxis
- Cardiac- atrioventricular heart block, cardiac arrest

- Neurologic- dizziness, altered mental status, seizure
- Miscellaneous

To assess if there are differences in the complications between the study groups.

- Length of Stay (days)

Length of stay in the hospital can be used as downstream marker of overall postoperative course. It is limited by attending practice patterns.

- Total Opioid Prescription at Discharge (morphine equivalents in mg)

To assess if there are differences in the amount of opioid prescribed at discharge.

- Total Opioid Use as Outpatient (morphine equivalents in mg)

To assess if there are differences in the amount of opioid used after discharge.

- Direct Costs of Hospital Encounter (dollars)

The interventions in the study add costs over standard of care. It is important to evaluate the burden on the health care system in addition to subject outcomes.

- Quality of Life: Short-Form-8 Health Survey (Rand Health)

A change in quality of life before and after surgery will be assessed. This survey is limited by subject adherence to completion.

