9.1.6 Other Clinical Procedures

Subjects will be given the Short Form-8-Health Survey at the preoperative and postoperative clinic visits. In addition, subjects will be given a Pain Medication Survey at the postoperative clinic visit to capture what medications are still being used to control pain.

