10 EVALUATIONS BY VISIT

10.1 Visit 1 – Preoperative Clinic Visit

1. Review the study with the subject and obtain written informed consent and HIPAA authorization.
2. Assign the subject a unique screening number.
3. Record demographics data.
4. Record medical history, including indication for surgery and prior thoracic surgeries.
5. Record concomitant medications.
6. Perform a complete physical examination.
7. Perform and record vital signs.
8. Obtain routine preoperative studies as clinically indicated, including pulmonary function tests, cardiology evaluation, chest imaging (CT, PET-CT, MRI), bronchoscopy with endoscopic ultrasound, and lung biopsy.
9. Administer Short Form-8-Health Survey
10. Schedule subject for surgery.

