10.2 Visit 2 – Surgery with Hospitalization

1. Collect urine pregnancy test in female patients of childbearing age in the preoperative suite.
2. Randomize to Liposomal Bupivacaine or Standard Bupivacaine during surgery.
3. Administer intervention during surgery.
4. Record any Adverse Experiences and/or Review subject diary for adverse experiences and exclusionary medication use daily.
5. Concomitant medications administration.
6. Perform abbreviated physical examination daily.
7. Perform and record vital signs every 4 hours.
8. Monitor with Continuous Pulse Oximetry and Continuous Cardiac Monitoring throughout hospitalization.

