15.3 Analysis of Primary Endpoint

Null Hypothesis: There is no difference in cumulative in-hospital use of opioids in subjects who receive intercostal nerve block and wound infiltration Liposomal Bupivacaine or Standard Bupivacaine during minimally invasive lung resection.

Student's t-test will be used to assess the means of the cumulative total of in-hospital oral morphine equivalents. It is presumed that the data will be normally distributed. If this assumption is not met, transformation or nonparametric tests (Mann-Whitney U test) will be used. Moreover, as there are only 40 subjects per group, it is possible that we do not achieve effective randomization. If this occurs, we will utilize linear regression adjusting for age, sex, race, comorbidity, diagnosis, and procedure performed. A power of 0.8 and 2-sided alpha error set at 0.05 will be used to assess for statistical significance.

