15.4 Analysis of Secondary Endpoints

- Cumulative Daily In-Hospital Pain Score (0-10)
- Mean Time to First Opioid Use (hours)
- Mean Time to Ambulation (hours)
- Pulmonary Complications: Pneumonia and Atelectasis requiring Bronchoscopy (y/n)
- Liposomal Bupivacaine and Stand Bupivacaine Adverse Events (y/n):
 - Gastrointestinal- nausea, emesis, constipation
 - Hypersensitivity- pruritis, urticaria, anaphylaxis
 - Cardiac- atrioventricular heart block, cardiac arrest
 - Neurologic- dizziness, altered mental status, seizure
 - Miscellaneous

Safety and tolerability data will be summarized by treatment group. Adverse event rates will be coded by body system and will include the number of patients for whom the event occurred, the rate of occurrence, and the severity and relationship to study drug.

- Length of Stay (days)
- Total Opioid Prescription at Discharge (morphine equivalents in mg)
- Total Opioid Use as Outpatient (morphine equivalents in mg)
- Direct Costs of hospital encounter (dollars)
- Quality of life – Short-Form-8 Health Survey (Optum Health)

Student's t-test, Pearson's chi-squared test, and Kaplan-Meier survival estimate will be used. A 2-sided alpha error set at 0.05 will be used to assess for statistical significance.

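### SF-8 quality of life appears to be compared without adjusting for the baseline score already collected; regression on baseline would usually be more precise

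*Combined protocol and SAP*

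**What the plan says.** Quality of life is part of the secondary objective (Section 3.2). Section 5.2 defines the SF-8 endpoint in one sentence: "A change in quality of life before and after surgery will be assessed".

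The data for a baseline adjustment are already planned. Section 9.1.6 states: "Subjects will be given the Short Form-8-Health Survey at the preoperative and postoperative clinic visits". Section 10.1 repeats the survey for Visit 1, and Section 10.3 for Visit 3. Section 10.2 places allocation at Visit 2: "Randomize to Liposomal Bupivacaine or Standard Bupivacaine during surgery". The Visit 1 score therefore precedes randomisation and is a proper covariate.

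Section 15.4 lists ten secondary endpoints, SF-8 among them, and gives one sentence on method for all of them: "Student's t-test, Pearson's chi-squared test, and Kaplan-Meier survival estimate will be used". It does not match tests to endpoints. Regression appears only in Section 15.3, for the primary opioid endpoint, and only if randomisation is judged not to have worked. There the plan says "we will utilize linear regression adjusting for age, sex, race, comorbidity, diagnosis, and procedure performed", a list that does not include baseline SF-8. Section 15 defers detail to a later SAP. The documents contain no further text on how SF-8 will be analysed.

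**The concern.** Of the three methods in Section 15.4, only the t-test fits a continuous score. Read with Section 5.2, the natural analysis is a t-test on the change from Visit 1 to Visit 3. The wording would also allow a t-test on the Visit 3 score alone.

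Both use the baseline with a fixed weight. A change score subtracts the whole baseline value (weight 1), and the postoperative score ignores it (weight 0). Regression on baseline estimates the weight from the data. If the pre/post correlation is moderate, subtracting the whole baseline adds noise and ignoring it discards information. What is at stake is the width of the confidence interval for the quality-of-life comparison, with 40 patients per arm and no new data needed to narrow it. Because the plan does not say which score is tested, that choice is also still open.

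**Working it through.** **Inputs from the documents.** 80 patients, 1:1, so 40 per arm (Section 15.6); two-sided alpha 0.05 for secondary endpoints (Section 15.4); SF-8 at Visits 1 and 3 (Section 9.1.6). The plan states no power or precision figure for SF-8, so there is none to reproduce. The calculation in Section 15.6 concerns opioid use and is not needed here.

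**Assumptions.** The documents give no SF-8 standard deviation, pre/post correlation, target difference or completion rate. Let s be the SD at Visit 3 and rho the within-arm correlation between visits. I take equal variance at both visits first, then relax it, and assume complete pairs throughout.

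**Step 1: change score against ANCOVA, equal variances.** Per patient:
- change score: 2s²(1 − rho)
- ANCOVA: s²(1 − rho²)
- ratio ANCOVA/change: (1 + rho)/2

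Estimating the slope multiplies the ANCOVA variance by about 1 + 1/(80 − 4) = 1.013.

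| rho | ratio | ratio with slope penalty | fall in standard error | change-score patients equivalent to 80 under ANCOVA |
|---|---|---|---|---|
| 0.3 | 0.65 | 0.66 | 18.8% | 121 |
| 0.5 | 0.75 | 0.76 | 12.8% | 105 |
| 0.7 | 0.85 | 0.86 | 7.2% | 93 |
| 0.9 | 0.95 | 0.96 | 1.9% | 83 |

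A simulation of 20,000 trials with 40 per arm gave ratios of 0.67, 0.77, 0.87 and 0.96. With the penalty, ANCOVA is ahead until (1 + rho)/2 × 77/76 = 1, that is rho = 152/77 − 1 = 0.97.

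**Step 2: power, for illustration only.** Assume a true difference of 0.5s and 40 complete pairs per arm. Power at rho 0.3, 0.5 and 0.7 is 46%, 60% and 81% for the change-score t-test, and 64%, 72% and 87% for ANCOVA (before the slope penalty).

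**Step 3: unequal variances.** Let the Visit 3 SD be k times the Visit 1 SD. The ratio becomes k²(1 − rho²)/(1 + k² − 2·rho·k). At k = 1.4:
- rho 0.3: 1.784/2.12 = 0.84
- rho 0.5: 1.47/1.56 = 0.94
- rho 0.7: 0.9996/1.00 = 1.00

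The denominator minus the numerator is (1 − rho·k)², which is never negative. So, apart from the slope penalty, ANCOVA is never less precise, but its gain vanishes where rho·k = 1. At k = 1.4 and rho 0.7, rho·k = 0.98, and after the penalty ANCOVA is about 1.3% worse in variance.

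**Step 4: if the t-test is on the Visit 3 score alone.** The ratio ANCOVA/post is 1 − rho²: 0.91, 0.75, 0.51 and 0.19 at rho 0.3, 0.5, 0.7 and 0.9, before the same penalty. With equal variances, the change score is itself less precise than the Visit 3 score alone when 2(1 − rho) exceeds 1, that is when rho is below 0.5.

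**Step 5: bias or variance?** With equal variances, given a chance baseline difference D between arms, the change-score estimate is off by −(1 − rho)D. Over repeated randomisations D averages zero. The variance that this term adds is already counted in Step 1, because 2(1 − rho) = (1 − rho²) + (1 − rho)². At rho 0.5 this reads 1.00 = 0.75 + 0.25.

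**The case against.** The strongest reply is that the planned test is sound, the gain is of unknown size, and a later SAP can settle the matter.

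- **The test on change is inferred.** A reader might take the plan to specify a t-test on SF-8 change. It does not: Section 15.4 never ties a test to an endpoint. This stands, and it limits the wording to what the plan appears to do. The point survives, because the alternative in Step 4 also leaves baseline unadjusted.
- **Bias.** A reader might infer that chance baseline imbalance biases the change-score comparison through regression to the mean. Under randomisation it does not. The shift is conditional on the imbalance observed, and Step 5 shows it is part of the variance already counted. The argument is one of efficiency only.
- **Size of the gain.** Everything depends on rho and on equal spread at the two visits, neither of which is documented. Surgery between the visits could change the spread. Step 3 shows the gain falling to nothing in a plausible case, so no single figure for patients saved can be given.
- **Low power.** A reader might conclude that the quality-of-life comparison has little power. The documents give no basis for that: under the Step 2 assumptions the change score reaches 81% at rho 0.7. Section 5.2 warns that survey completion depends on the subjects, but gives no rate.
- **Later SAP.** Section 15 allows the SAP to modify the plan. That is a good place for the correction, but it does not supply the method now.

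**Conclusion.** The point holds as an efficiency improvement of low severity. Sections 5.2 and 15.4 together appear to compare SF-8 by an unadjusted t-test, although a baseline score is collected before randomisation. The comparison is valid as it stands, but generally less precise than regression on baseline.

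Under equal variances and complete pairs, the variance falls by 35% at rho 0.3 and by 5% at rho 0.9, before the small slope penalty. It may not fall at all if the postoperative SD is clearly larger than the baseline SD. The conclusion rests on reading the two sections together and on assumed values of rho and k. It concerns one of ten secondary endpoints and does not touch the primary analysis.

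**What to change.** In Section 15.4, or in the SAP before the data are seen, state that the Visit 3 SF-8 score(s) will be compared between arms by linear regression on treatment with the corresponding Visit 1 score as covariate, and that the adjusted difference will be reported with its 95% CI. The plan should name the score or scores it will use, since the documents name only the survey.

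The cost is one sentence and one degree of freedom, about 1.3% of variance with 80 patients. No additional data or visits are needed. Missing postoperative surveys are a separate matter: this change does not recover them, and the plan would still need to say how they are handled.

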5.3 Safety Evaluations

All subjects will be monitored for cardiac arrhythmias with continuous cardiac telemetry throughout the entirety of their hospitalization per standard postoperative care. If cardiac arrhythmias occur, they will be managed by the surgery inpatient team and cardiology consultation if deemed necessary.

The mental status of each subject will be assessed daily by the surgery inpatient team and each shift (every 12 hours) by the nursing staff. Workup and management of altered mental status is at the discretion of the surgery team.

Surgical wounds will be monitored daily by the surgery inpatient team and each shift (every 12 hours) by the nursing staff. Evidence of hypersensitivity reaction will be treated with observation, antihistamines, and/or epinephrine depending upon the severity of reaction.

The minimum duration of inpatient monitoring is 24 hours. For subjects that are discharged on POD1 after 24 hours of monitoring, a safety assessment will be performed by telephone on POD2. If subject answers “Yes” to any of the questions, the subject will be brought into clinic for further evaluation. See *POD2 Safety Assessment* below for more information.

Adverse events will be assessed continuously, starting with the first patient enrollment and until study completion, and will be immediately reported to the Medical Monitor. Serious and severe adverse events, regardless of causality, will be followed until resolution or stabilization per Section 11 below.

Subjects will be discharged with specialized discharge instructions to alert them of potential adverse effects and instruct them when to call the clinic.

POD2 Safety Assessment

The safety assessment will be conducted over the phone on POD2 for subjects that were discharged on POD1. If the subject answers “yes” to any of these questions, the event will be recorded as an AE and the patient will be brought into clinic for further evaluation.

- Is the subject oriented?

_ Yes _ No _ Not Assessable

- Since your last assessment have you had numbness of the lips, the tongue, or around the mouth?

_ Yes _ No

- Since your last assessment have you had a metallic taste in your mouth?

_ Yes _ No

- Since your last assessment, have you had problems with your hearing not related to the use of a hearing aid?

_ Yes _ No

- Since your last assessment, have you had problems with your vision not related to the use of eye glasses?

_ Yes _ No

- Since your last assessment, have your muscles been twitching?

_ Yes _ No

- Since your last assessment, have you had heart palpitations in which you can feel your heart beating irregularly?

_ Yes _ No

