| CONCOMMITANT MEDICATIONS | 
Allowed:
 
Standardized Hospital Pain Medication Regimen
 
All subjects will receive a standardized postoperative pain regimen. Goal pain management is to allow the subject to ambulate and perform incentive spirometry per standard care. Escalation of opioid dosing if needed will be at the discretion of the inpatient surgery team.
 
Standardized Discharge Pain Medication Regimen
 
All subjects to be discharged on a standardized pain regimen.
 
Prohibited:
 
None
 |
| EFFICACY EVALUATIONS | |
| PRIMARY ENDPOINT | 
 • Cumulative Daily In-Hospital Use of Opioids (morphine equivalents in mg) |
| SECONDARY ENDPOINTS | 
 • Cumulative Daily In-Hospital Pain Score (0-10) • Mean Time to First Opioid Use (hours) |

| | |
|---|---|
| | 
 • Mean Time to Ambulation (hours) • Pulmonary Complications (y/n) • Liposomal & Standard Bupivacaine Adverse Events (y/n) • Total Opioid Prescription at Discharge (morphine equivalents in mg) • Total Opioid Use as Outpatient (morphine equivalents in mg) • Length of Stay (days) • Direct Costs of Hospital Encounter (dollars) • Quality of Life: Short-Form-8 Health Survey |
| OTHER EVALUATIONS | n/a |
| SAFETY EVALUATIONS | 
 - All subjects will be monitored with continuous cardiac telemetry throughout the entirety of their hospitalization. - Nursing staff will assess the mental status of each participant at the start of each shift. - Surgical wounds will be monitored daily by the surgery inpatient team. - The minimum duration of inpatient monitoring is 24 hours. For subjects that are discharged on POD1 after 24 hours of monitoring, a safety assessment will be performed on POD2. - Adverse events will be assessed continuously, starting with the first patient enrollment and until study completion, and will be immediately reported to the Medical Monitor. - Serious and severe adverse events, regardless of causality, will be followed until resolution or stabilization. - Subjects will be discharged with specialized discharge instructions to alert them of potential adverse effects and instruct them when to call the clinic. |

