9 STUDY PROCEDURES AND GUIDELINES

A Schedule of Events representing the required testing procedures to be performed for the duration of the study is diagrammed in Appendix 1.

Prior to conducting any study-related activities, written informed consent and the Health Insurance Portability and Accountability Act (HIPAA) authorization must be signed and dated by the subject.

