11 ADVERSE EXPERIENCE REPORTING AND DOCUMENTATION

11.1 Adverse Events

An adverse event (AE) is any untoward medical occurrence in a clinical investigation of a patient administered a pharmaceutical product and that does not necessarily have a causal relationship with the treatment. An AE is therefore any unfavorable and unintended sign (including an abnormal laboratory finding), symptom or disease temporally associated with the administration of an investigational product, whether or not related to that investigational product. An unexpected AE is one of a type not identified in nature, severity, or frequency in the current Investigator's Brochure or of greater severity or frequency than expected based on the information in the Investigator's Brochure.

The Investigator will probe, via discussion with the subject, for the occurrence of AEs during each subject visit and record the information in the site's source documents.

Adverse events will be recorded in the patient CRF. Adverse events will be described by duration (start and stop dates and times), severity, outcome, treatment and relation to study drug, or if unrelated, the cause.

AE Severity

The National Cancer Institute's Common Terminology Criteria for Adverse Events (CTCAE) Version 3.0 will be used to assess and grade AE severity, including laboratory abnormalities judged to be clinically significant. The modified criteria can be found in the study manual. If the experience is not covered in the modified criteria, the guidelines shown in Table 1 below should be used to grade severity. It should be pointed out that the term "severe" is a measure of intensity and that a severe AE is not necessarily serious.

Table 1. AE Severity Grading

| Severity (Toxicity Grade) | Description |
|----------------------------------|---|
| Mild (1) | Transient or mild discomfort; no limitation in activity; no medical intervention or therapy required. The subject may be aware of the sign or symptom but tolerates it reasonably well. |
| Moderate (2) | Mild to moderate limitation in activity, no or minimal medical intervention/therapy required. |
| Severe (3) | Marked limitation in activity, medical intervention/therapy required, hospitalizations possible. |
| Life-threatening (4) | The subject is at risk of death due to the adverse experience as it occurred. This does not refer to an experience that hypothetically might have caused death if it were more severe. |

AE Relationship to Study Drug

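### The POD2 telephone script acts only on a 'Yes', but 'Yes' is the normal answer to its orientation item, so 'No' and 'Not Assessable' lead to no scripted clinic evaluation

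*Combined protocol and SAP*

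**What the plan says.** The synopsis (Safety Evaluations) sets the requirement: "For subjects that are discharged on POD1 after 24 hours of monitoring, a safety assessment will be performed on POD2". Section 5.3 adds that this is done by telephone, and it states the action rule twice.

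- In the body of 5.3, a *Yes* "to any of the questions, the subject will be brought into clinic for further evaluation".
- Under the POD2 Safety Assessment subheading, a *yes* "to any of these questions, the event will be recorded as an AE and the patient will be brought into clinic for further evaluation".

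Neither sentence exempts an item. Seven items follow. The first is "Is the subject oriented", with the options *Yes*, *No* and *Not Assessable*. The other six ask about new symptoms and offer *Yes* or *No*; a typical one is "Since your last assessment, have your muscles been twitching".

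Altered mental status is a named adverse event in the secondary endpoints (5.2, repeated in 15.4): "Neurologic- dizziness, altered mental status, seizure".

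**The concern.** The action rule and the first item point in opposite directions. The rule treats *Yes* as the abnormal answer, while the orientation item treats it as the normal one. The finding that should bring a subject back, disorientation at home about a day after discharge, is recorded as *No*, and the printed rule does nothing with a *No*. *Not Assessable* is a foreseeable answer on a telephone call, and it also has no action.

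The call is the safeguard for subjects who leave after as little as 24 hours of monitoring. Section 1.1 says that drug levels can be detected for up to 96 hours, so POD2 lies within the exposure period. Section 2.1 lists altered mental status among the less common adverse events. At stake are the follow-up of an individual subject and, to a lesser degree, consistent coding of a neurologic event that the plan compares between groups.

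**Working it through.** The plan gives no figure to reproduce, so the check is one of logic: compare the printed trigger with the direction of each item.

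**Step 1. Direction of each item (5.3).**

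| Item | Subject matter | Abnormal answer | Answer that triggers action |
|---|---|---|---|
| 1 | Orientation | No | Yes |
| 2 | Numbness around the mouth | Yes | Yes |
| 3 | Metallic taste | Yes | Yes |
| 4 | Hearing | Yes | Yes |
| 5 | Vision | Yes | Yes |
| 6 | Muscle twitching | Yes | Yes |
| 7 | Palpitations | Yes | Yes |

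Rule and item agree for 6 of 7 and disagree for 1 of 7.

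**Step 2. Does item 1 fall under the rule?** The rule speaks of the subject answering. Items 2 to 7 address the subject directly, but item 1 is in the third person and has a *Not Assessable* box, so it may be the caller's rating. Both readings have to be followed through.

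| Answer to item 1 | Reading A: item 1 is under the rule | Reading B: item 1 is caller-rated, outside the rule |
|---|---|---|
| Yes (normal) | AE record and recall | No action |
| No (abnormal) | No action | No action |
| Not Assessable | No action | No action |

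Under A, 1 of 3 answers has an action, and it is the normal one. Under B, 0 of 3 have an action. The two lower rows are the same under both readings, so the conclusion about *No* and *Not Assessable* does not depend on which is right.

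**Step 3. Does other text supply the missing action?**

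- The synopsis says only that the assessment takes place.
- The sentence in 5.3 that leaves work-up of altered mental status to the surgery team follows the daily and per-shift inpatient checks. It is not tied to the call.
- Section 11.1 defines an AE to include "any unfavorable and unintended sign (including an abnormal laboratory finding), symptom or disease temporally associated with the administration of an investigational product". That would cover disorientation noticed on the call, but a definition does not bring anyone into clinic.
- Section 5.3 requires AEs to be reported immediately to the Medical Monitor. That brings in a physician but does not script an evaluation.
- Visit 3 (10.3) includes AE recording and an abbreviated physical examination, but no orientation question.

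None of these attaches a clinic evaluation to a *No* or *Not Assessable* on item 1.

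**The case against.** The strongest reply is that this is a drafting slip that any nurse or physician making the call would correct. Being oriented is not an untoward occurrence under 11.1, so nobody would sensibly record it as an AE. A caller who found a subject disoriented would have a named AE to report at once to the Medical Monitor. Severe or serious events are followed to resolution or stabilization, and discharge instructions tell subjects when to call. Most of this stands. It makes harm unlikely and keeps the point minor. It does not supply the missing instruction, and a safety script should not rely on callers to reverse it.

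Three stronger inferences are tempting, and the documents do not support them.

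- *Every oriented day-1 discharge becomes a false AE and a recall.* This follows only under reading A applied to the letter. Under reading B the number is zero. The share discharged on day 1 is not given: assumed shares of 10%, 25% or 50% of 80 subjects would give 8, 20 or 40 as upper bounds, which shows only that the count cannot be derived from the documents.
- *Disorientation after discharge would go undetected.* The call is the only scheduled contact after discharge with an explicit orientation question, but it is not the only opportunity. Visit 3 and general AE capture remain.
- *The call is not really required because the schedule omits it.* Section 9 says "A Schedule of Events representing the required testing procedures to be performed for the duration of the study is diagrammed in Appendix 1", and the call is missing from there and from Section 10. But Appendix 1 also omits the SF-8 and the Pain Medication Survey, which Section 10 requires. The omission is housekeeping and does not cancel a requirement stated in the synopsis and in 5.3.

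**Conclusion.** The point holds and is minor. As printed, the only trigger for recall and an AE record does not fit item 1, and on either reading an abnormal or unassessable orientation answer has no scripted clinic evaluation. The fault is confined to one item of seven and to subjects discharged on day 1. The documents do not say how many of those subjects would be disoriented on POD2, which is the number that would measure the clinical consequence.

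The primary endpoint, sample size, error rate and allocation are not affected. The script is the same in both blinded arms, so nothing here implies a bias towards one treatment. The likely practical result is some inconsistent coding and an occasional missed or unneeded recall.

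The conclusion rests on the visible text. The case report form and the study manual are not part of the documents, and Section 11.4 (Medical Monitoring), listed in the table of contents, was not in the text available, so a correction in one of those places cannot be ruled out.

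**What to change.** Amend both trigger sentences in 5.3 so that they state the same rule:

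- *No* on orientation, if new or worse than the preoperative baseline, or *Yes* on any of the other six items, is recorded as an AE and brings the subject into clinic.
- *Not Assessable* leads to a repeat call the same day or contact with a caregiver. If the question is still unresolved, the investigator decides on a clinic visit.

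The baseline qualifier is needed because 6.2 allows consent by a legal representative and no criterion in 6.3 names cognitive impairment, although criterion 10 leaves room for judgement. Without the qualifier, long-standing disorientation would be coded as a new AE. Orientation is not a named item at Visit 1, so a short note in the complete physical examination there would give the caller something to compare with.

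The cost is one wording amendment, the baseline note, and an occasional repeat call or caregiver contact. Listing the POD2 call in Section 10 and Appendix 1 in the same amendment is optional housekeeping.
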